4. STUDY DESIGN

4.1 General design

This clinical study will be a multicentre, prospective, controlled study, whose aim is to evaluate the clinical efficacy of a battery-powered portable device that uses blue LEDs.

As described in greater detail in the statistical analysis section, at least a 20% difference between treated and untreated wounds is expected to be observed in the same patient within the specified observation period.

For safety, the operator will be equipped with UV protection glasses. The housing of the device is made of biocompatible material that can be disinfected with detergents commonly used in hospitals in order to prevent contamination.

The device passed all safety tests (electrical, electromagnetic and photobiological) required by current regulations on medical devices, as well as a precise risk and usability analysis, and was found to be suited to the intended use.

The treatment, which is provided in addition to the patient's standard therapy, will be performed at each visit for 60 seconds on each 5-cm diameter sub-area of the selected wound or part of it.

Therefore, for multiple wounds, one will be treated with the EmoLED device and one will be selected as a control wound; very large wounds will be divided into two halves and one of the two will be the control wound. This will reduce any variability associated with randomised clinical trials (RCTs) on skin ulcer conditions.

4.1.1 Selection of the treatment area.

All wounds will be cleaned with saline solution and, if there is slough/black eschar, surgical debridement will be performed using a scalpel. Only at this point will treatment with the EmoLED device take place.

If a patient has more than one wound and all wounds at enrolment are found to have a **diameter of less than 5 cm**, the worst of the wounds will be treated entirely with the EmoLED device, whereas the others will serve as control wounds. Progression of all wounds will be evaluated over the ten-week study duration.

By contrast, if a wound at recruitment has a **diameter greater than 5 cm**, the wound will be divided into two halves along the longest side, and only one of the two halves will be treated. The other half of the wound will be dressed with a multi-layered sterile dressing. The division line between the two halves of the wound will be marked with a permanent marker, which will be reapplied at each visit, or whenever it begins to fade, to prevent loss of the reference marks.

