If, at recruitment, a patient has more than one wound with a **diameter greater than 5 cm**, all wounds will be divided into two halves along the longest side and treated as described above.

After treatment with the EmoLED device, the wound will be dressed with a hydrofibre dressing. If clinical signs of infection occur, the wound will be dressed with a hydrofibre dressing with silver. The limb will then be bandaged with a compression bandage.

4.1.2 Standard treatment and data recording.

Any wounds or parts of wounds that are not treated with the EmoLED device will be medicated using the standard treatment consisting of a hydrofibre dressing or hydrofibre dressing with silver (as described above) and compression therapy. Ultimately, the treatment differs only for the fact that the EmoLED device is used in accordance with the procedure described above, while the rest of the treatment remains unchanged.

Following enrolment and the signing of the Informed Consent Form, the pertinent data from each patient will be recorded in the respective Case Report Form according to the following schedule: W0 (Week 0: enrolment and first treatment), W1, W2, W3 ... to W10, as per the routine visits over the 10-week period from enrolment.

Patients may miss a maximum of two non-consecutive follow-up visits over the 10-week period, starting from visit 5. Patients will be excluded from the study if consecutive visits are missed.

The parameters used to define the study outcomes will be based on:

- photographic images of the wounds treated with the EmoLED device as well as of control wounds
- Case Report Form completed by the doctor during the visits.

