6. STATISTICAL PLAN

Ninety subjects will be enrolled in this study. Each subject is part of both the control group and the treatment group.

Given that each patient will both receive the treatment and will also be a control subject, both groups will contain the same number of subjects, even if some of the subjects withdraw from the study. A comparative study of the subjects' demographic data and other baseline characteristics will also not be necessary as the two groups will be perfectly superimposable.

Treatment will be administered immediately after the cleaning and any necessary debridement of the complete wound. The area of the wound that should not be treated with the EmoLED device will be duly marked and covered with different layers of sterile dressing; this facilitates treatment standardisation and uniformity, thereby limiting any variability; it will also enable the treated, untreated and adjacent areas of each subject to be coherently defined.

The aim of the statistical analysis will be to establish the efficacy of the treatment with the EmoLED device; the significance ($p<0.05$) of any difference observed in the healing process between treated and untreated areas will be evaluated. Specifically, the primary endpoint of the study is the percentage reduction of the area of the wound treated with the EmoLED device versus the wound not treated with the EmoLED device at W10.

The secondary endpoints are:

1. Treatment safety.
2. Outcomes comparison in terms of the percentage reduction of the area of the wound treated with the EmoLED device versus the wound treated with SOC only within the ten-week observational period.
3. Evaluation of difference in healing time between the two areas.
4. Pain reduction (with pre-treatment assessment on a 0-10 VAS)
5. (OPTIONAL) Depending on the patient's willingness to continue to go to the study site, the observation of any unhealed area(s) over the 10-week period can be extended until complete healing or up to 20 weeks.

Estimation of sample size

The considerations underlying the choice of the model described below were drawn from a review of the literature on leg ulcer therapies and healing dynamics as well as on past clinical experience data obtained by the sites involved in the study with the treatment in question.

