The most significant finding yielded by the analysis of the clinical data in our possession is an expected 30% variability in the percentage reduction of the area of the wound at week 10. This value was confirmed by [15], where it was used to estimate the sample size. On the other hand, [16] found the standard deviation of the percentage reduction of the area of the wound to be 53% in the worst case and limited to venous ulcers only.

The analysis for the calculation of the sample size is based on:

- the clinical objective, which is represented by the percentage reduction of the area of the wound at W10
- a non-parametric statistical instrument for paired data, namely the Wilcoxon signed-rank test
- an a priori hypothesis of expected variability of 50% (conservative value)
- an expected 20% mean difference in the percentage reduction between the treated and the non-treated area
- a statistical power of 80% ($\beta=0.2$) and $\alpha=0.05$ will be considered
- a unilateral alternative hypothesis: the EmoLED treatment does not result in worsened outcome
- A correlation coefficient between percentage reductions of the treated and untreated area of 0.1, 0.3, 0.5 and 0.7
- A method for estimating the sample size based on asymptotic relative efficiency, compared to the t-test (minARE)

| | Estimate 1 | Estimate 2 | Estimate 3 | Estimate 4 |
|---|------------|------------|------------|------------|
| β | 0.2 | 0.2 | 0.2 | 0.2 |
| α | 0.05 | 0.05 | 0.05 | 0.05 |
| Diff. in % wound area reduction after 70 days | 20% | 20% | 20% | 20% |
| ρ | 0.1 | 0.3 | 0.5 | 0.7 |
| n | 83 | 65 | 47 | 29 |

The higher estimate is that relating to case 1, whose sample size is 83 subjects, which served as the basis for the choice of the number of subjects to be recruited, taking into account possible loss of subjects during treatment.

Statistical analysis of the primary endpoint.

A Wilcoxon signed-rank test with a significance level of 0.05 will be performed to evaluate the efficacy of use of the device. This test allows paired data to be handled and is robust enough to evaluate variability in observation distribution. A population analysis, as well as a per-protocol analysis (PP), will be performed for the subjects who complete the study.

Statistical analysis of secondary endpoints.

1. Treatment safety.

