Adverse event reports will be collected, analysed and managed according to the criteria indicated in 5.2. The most appropriate statistical instrument will be chosen for analysis based on the number and type of adverse events reported.

2. Outcomes comparison as percentage reduction of the area of the wound treated with the EmoLED device versus the wound treated with SOC alone during the 10-week observation period.

Both the areas of the wound treated with the EmoLED device and those not treated with the EmoLED device, as measured on the required observation days, will be considered. A statistical analysis of paired data will be

performed using repeated measurements. In particular, both a comparison of the measurements obtained on different days, separately, and an analysis that will take into account the global trend over the observation period, will be performed.

Tests for data paired to pairs of measurements obtained on different observation days will be performed in the first case. These tests will be applied separately to the various days, evaluating any significant differences in both treated and untreated areas. The adopted statistical test will be either a parametric (t-test) or a non-parametric test (Wilcoxon signed-rank test) depending on the observed data distribution. The statistical significance will be corrected for multiple comparisons (e.g., given the possibility of a positive correlation between the identified measurements, Benjamini-Hochberg correction will be considered).

In the second case, the area under the curve (AUC) will be evaluated for each subject and in each area in order to obtain information on possible differences between changes in the treated and untreated areas of the wound. Either parametric or non-parametric paired data tests (depending on parameter distribution) will be performed in order to evaluate any differences in the trends of this parameter summarising the healing dynamics both in the treated and untreated areas.

The mean value observed in the remaining subjects will be used for both approaches if there is any missing data. A sensitivity analysis will be performed using both the best value and the worst value observed in the subjects.

3. Evaluation of the difference in healing time between the two areas.

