A survival analysis will be performed based on the Akritas test applied to the Kaplan-Meier curve. This type of analysis is used to evaluate the time from observation to the event of interest (time-to-event). In particular, in this case, the event will be a percentage reduction of the area of the wound of $\geq 70\%$ at W10. This approach will allow both paired data and the possibility that some of the subjects may be non-adherent to the protocol and withdraw from the study to be managed. A curve will be constructed for each group, each corresponding to the analysis of the two areas, both that treated with the EmoLED device and that not treated with the EmoLED device. The Akritas test is based on a transformation into ranked "survival" times, understood as time to event of interest (time-to-event). In particular, in this case, the event will be a percentage reduction of the area of the wound of at least 70% at W10. Ranked observations will be transformed according to a model that takes into account the possibility that they may be truncated or censored.

4. Pain reduction (pre-treatment assessment on a 0-10 VAS).

A non-parametric analysis will be performed using the Friedman test, which can be considered the non-parametric equivalent of the ANOVA test for repeated measurements.

5. (OPTIONAL) Depending on the patient's willingness to continue to go to the study site, the observation of any unhealed area(s) over the 10-week period can be extended until complete healing or up to 20 weeks.

The analysis will be performed as for endpoint 2.

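### Pain (secondary endpoint 4) is planned only as a Friedman test with no between-area contrast or scoring unit; read over visits, it cannot attribute a fall in pain to EmoLED

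*Combined protocol and SAP*

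**What the plan says.** - **Endpoint.** Sections 4.3 and 6 define endpoint 4 as "Pain reduction (with pre-treatment assessment on a 0-10 VAS") and add nothing. No area, comparator or visit is named, and it is not said whether pre-treatment means W0 or before each weekly session.
- **Analysis.** Item 4 of the secondary analyses in section 6 is one sentence: a non-parametric analysis "will be performed using the Friedman test, which can be considered the non-parametric equivalent of the ANOVA test for repeated measurements".
- **Neighbouring endpoints.** Endpoint 2 names EmoLED versus standard care, and endpoint 3 names the two areas. Endpoint 4 names neither.
- **General aim (section 6).** The significance "of any difference observed in the healing process between treated and untreated areas will be evaluated".
- **Design.** "Each subject is part of both the control group and the treatment group" (section 6). On care, section 4.1.2 says: "Ultimately, the treatment differs only for the fact that the EmoLED device is used in accordance with the procedure described above".
- **Allocation (section 4.1.1).** Where a patient has several wounds, all under 5 cm, "the worst of the wounds will be treated entirely with the EmoLED device, whereas the others will serve as control wounds".
- **Missing data.** Under endpoint 2: "The mean value observed in the remaining subjects will be used for both approaches if there is any missing data". The two approaches meant are those of endpoint 2, so no rule is given for pain. Section 4.1.2 tolerates up to two non-consecutive missed visits from visit 5 onward, and section 2 ends monitoring at healing if that comes before W10.
- **Primary endpoint tool.** The sample-size section uses "a non-parametric statistical instrument for paired data, namely the Wilcoxon signed-rank test".

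**The concern.** The trial exists to separate EmoLED from standard care within the same patient, yet the pain sentence contains nothing that does so. The reference to repeated measurements points to visits as the Friedman factor. Dressings and compression go to both areas and may themselves reduce pain, so a significant result over visits would be expected even if the device had no effect on pain. If that result were then read as device-related relief, the reading would have no support in the analysis. The missing scoring unit matters as much: if the VAS is one score per patient, no method can compare the areas. The Friedman test also needs a complete set of visits per patient, and the plan does not say what happens when there are gaps.

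**Working it through.** The plan gives no pain figure to reproduce. Its sample sizes of 83/65/47/29 belong to the primary endpoint. They reproduce exactly (one-sided paired t-test, effective n = 0.864n) and have no bearing on pain.

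**1. What each reading tests.** Write the VAS of patient i, area j, visit t as

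Y(i,j,t) = P(i) + A(i,j) + m(t) + d(t)·[j = EmoLED] + e(i,j,t),

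where m is the course on standard care and d the device effect.

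- *Friedman over visits in the treated area:* the null is that m(t) + d(t) is constant. m and d cannot be separated.
- *Friedman over all 2 × 11 = 22 area-by-visit cells:* a changing m(t) alone breaks the null.
- *Two areas, each patient-visit as a block:* A(i,j) persists across visits, so the blocks are not independent.
- *Two areas, patient as block, W0-W10 change as response:* P, A and m cancel. With two conditions the statistic is (b − c)²/(b + c) on 1 df, where b and c count patients whose treated area changed more or less than the control. This is the sign test.
- *Wilcoxon signed-rank test on* D(i) = [Y(i,E,10) − Y(i,E,0)] − [Y(i,C,10) − Y(i,C,0)]: the same cancellation leaves d(10) − d(0) plus noise.

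**2. Simulated rejection rates with no device effect.** The documents give no VAS mean, SD or correlation, so those inputs are assumed.

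*Set A:* 90 patients, 11 visits, VAS rounded to 0-10, mean 5, SD 2, visit correlation 0.6, linear fall shared by both areas, two-sided 0.05, no worst-wound selection.

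| Analysis | Fall 0 | 0.25 | 0.5 | 1 |
|---|---|---|---|---|
| Friedman over visits | 5% | 17% | 69% | 100% |
| Friedman over 22 cells | 9% | 20% | 77% | 100% |
| Wilcoxon on D | 3-7% in every setting run | | | |

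At a 0.5-point fall, Friedman over visits gives 47% at correlation 0.4, 97% at 0.8, and 48% at SD 2.5. The 22-cell figures also depend on the assumed correlation between areas.

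*Set B:* SD 2.5, with half the variance between patients, a quarter between areas and a quarter visit noise; 2-point fall in both areas. Friedman over visits and over 22 cells both reject 100%. Patient-visit blocks reject 38% (37% with no fall). Two-area Friedman on change rejects 4.6% (4.7% with no fall), so it holds its level. For an extra reduction of 0.5/1 point in the treated area, its power is 30/78%, against 38/89% for Wilcoxon on the same data.

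**3. Worst-wound allocation and the proposed test.** Assume 45 two-wound patients, wounds independent within patient, SD 2, visit correlation 0.6, and correlation r between being chosen as worst and pain. For two independent normal values the expected gap is 1.128 SD. If worst tracks the W0 score, the treated wound starts higher by r × 1.128 × 2 and regresses by (1 − 0.6) of that:

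- r = 0.3: 0.4 × 0.3 × 2.256 = 0.27 points
- r = 0.5: 0.4 × 0.5 × 2.256 = 0.45 points
- r = 0.8: 0.4 × 0.8 × 2.256 = 0.72 points

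All three favour EmoLED with no device effect. In simulation the unadjusted between-area change is then significant in its favour in 9/21/46% of trials. If worst tracks persistent pain instead, A cancels and the bias is about 0; adjusting for W0 would then bias against EmoLED by 0.22/0.38/0.74 points. Neither version is safe in both cases.

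**4. Incomplete visits.** Assume a miss probability p at each of W5-W10, keeping patients with at most two misses, none consecutive. Of the 15 possible pairs of visits, 5 are adjacent, leaving 10. At p = 0.05:

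- no miss: 0.95⁶ = 0.735
- one miss: 6 × 0.05 × 0.95⁵ = 0.232
- two misses: 10 × 0.05² × 0.95⁴ = 0.020
- incomplete share: 0.252/0.988 = 26%
- W10 missing: (0.05 × 0.95⁵ + 4 × 0.05² × 0.95⁴)/0.988 = 4.7%

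At p = 0.03/0.05/0.10, 16/26/44% of retained patients have an incomplete block and 3/5/9% lack W10. The W10 figures count missed visits only. Patients whose monitoring ends at healing also lack W10, in a number the documents do not give.

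**The case against.** A reader might infer that no Friedman analysis could validly compare EmoLED with standard care. The documents do not support that. The endpoint is named as a reduction, so ranking change is a fair reading, and the two-area version on change is a level-holding sign test. It needs per-area scoring, but so does the proposed Wilcoxon test. Choosing Wilcoxon over it is a matter of power, not validity. What remains is that the plan does not specify this reading.

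A reader might also take 69% or 100% as a false-positive rate. It is not: when pain falls, rejecting is the right answer to whether pain fell. Nor does the plan say that a significant pain result will be credited to the device. The harm would come from a later misreading.

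The general aim in section 6 is to establish the device's efficacy and leads into the endpoint list, so a between-area contrast for pain may be implied. That is arguable, but the sentence is worded for healing, and even a generous reading leaves the scoring unit, response and visit open. The case report form is not among the documents and may settle the scoring unit.

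Finally, worst-wound allocation is a design matter, not a defect of the Friedman test, and the proposed test is exposed to it too. That objection stands in full.

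**Conclusion.** The concern holds as a gap in specification with a practical consequence. On its natural reading the planned test shows only whether pain changed over time; it cannot isolate the device from care that both areas share. The simulated rates illustrate this and rest wholly on assumed VAS inputs. The pattern is the same under both input sets, but the size moves with SD and correlation.

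The proposed test is not free of problems. Its 3-7% rejection rate applies only without worst-wound selection, and it inherits the missing W10 scores of patients who heal early. The change should be made, but the point is limited to one secondary endpoint. The primary analysis and the sample size are unaffected.

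**What to change.** 1. State whether the VAS is scored per area or per patient. Record the pre-treatment VAS separately for treated and control area wherever the patient can tell them apart, and name one treated-control pair per patient, since section 4.1.1 allows several control wounds or several divided wounds.
2. Make the pain analysis a paired Wilcoxon signed-rank test on the between-area difference in W0-W10 change. Keep Friedman over visits as a descriptive within-area summary.
3. State how missed visits and visits after healing are handled for pain.
4. Report split-wound and multi-wound patients separately. Disclose that non-random worst-wound allocation can bias the multi-wound comparison, and use W0 adjustment only as a sensitivity analysis.
5. If the VAS is one score per patient, or the halves cannot be told apart, report pain over time descriptively and draw no conclusion on device-related relief.

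**Cost.** One extra VAS entry per visit and a few lines of SAP text. Fewer patients may contribute if the halves of a split wound cannot be distinguished: under Set A, power for a 1-point between-area difference is 94/69/52% with 90/45/30 contributing patients.

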4.3 Secondary endpoints

The following secondary endpoints were identified for this study:

1. Treatment safety.
2. Outcomes comparison in terms of the percentage reduction of the area of the wound treated with the EmoLED device versus the wound treated with SOC only within the ten-week observational period.
3. Evaluation of difference in healing time between the two areas.
4. Pain reduction (with pre-treatment assessment on a 0-10 VAS)
5. Depending on the patient's willingness to continue to go to the study site, the observation of any unhealed area(s) over the 10-week period can be extended until complete healing or up to 20 weeks.

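### Optional endpoint 5 inherits endpoint 2's mean-fill rule in a voluntary extension, which makes its paired tests anti-conservative, and the plan gives no convention for areas that have healed

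*Combined protocol and SAP*

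**What the plan says.** Section 4.3 and section 6 make the extension depend on the patient's "willingness to continue to go to the study site, the observation of any unhealed area(s) over the 10-week period can be extended", to complete healing or week 20. The only analysis sentence for it, in section 6 under secondary endpoint 5, is "The analysis will be performed as for endpoint 2".

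Endpoint 2 compares treated and control areas by paired t-test or Wilcoxon signed-rank test at each observation day, with a Benjamini-Hochberg correction, and also compares the area under the curve. Its missing-data rule is: "The mean value observed in the remaining subjects will be used for both approaches if there is any missing data". The only sensitivity analysis is: "A sensitivity analysis will be performed using both the best value and the worst value observed in the subjects".

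Section 4.1.2 bounds missing data in the main phase: "Patients may miss a maximum of two non-consecutive follow-up visits over the 10-week period, starting from visit 5". It then excludes patients who miss consecutive visits. Endpoint 5 has no missing-data rule, analysis set or healed-area convention of its own.

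**The concern.** A rule suited to occasional gaps in a scheduled ten-week phase is carried into a period where gaps are built in. Two things follow.

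- **Missing pairs.** A patient absent at a visit is given the treated-area mean and the control-area mean of those present. The filled within-patient difference is then the observed mean difference, identical for every absent patient. It adds to the sample size and adds no variation.
- **Healed areas.** Only unhealed areas are followed after week 10. If one area of a pair has healed and the other has not, only the second has a later measurement. The plan does not say what value the first takes.

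At stake is whether a reported week 11 to 20 difference can be trusted. The first problem overstates significance. The second, if the fill rule were applied to healed areas, would understate the effect and penalise the arm that heals more often.

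**Working it through.** **Inputs.** From section 6: 90 enrolled patients, each contributing both areas; the planning SD ("an a priori hypothesis of expected variability of 50% (conservative value"), 50 points; correlation 0.1 (the plan's most cautious case); a 20-point difference; alpha 0.05. Not in the documents, hence assumed: extension uptake, attendance at each visit, and mean reductions.

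**The plan's own figure.** SD of the difference = 50 × √(2 × (1 − 0.1)) = 67.08. One-sided paired t-test power of 80% for 20 points, with n multiplied by the minimum relative efficiency 0.864, gives n = 83. The other correlations give 65, 47 and 29. All four match the plan.

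**Step 1: the t-test after filling.** Let m of N pairs be observed, with SD of differences s, and let N − m be filled at the observed mean difference. The mean is unchanged and the variance becomes (m − 1)s²/(N − 1). Hence

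t(filled) = t(observed) × √[N(N − 1) / (m(m − 1))].

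True two-sided error = P(|T with m − 1 df| > t(0.975, N − 1) / factor).

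**Step 2: entrants only.** For N = 40 and m = 38, the factor is √(1560/1406) = 1.053 and the effective critical value is 2.023/1.053 = 1.920. Wilcoxon rates are simulated under no difference, with bivariate normal values, SD 50, correlation 0.1 and missingness unrelated to outcome.

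| Missing at visit | m of 40 / m of 60 | Factor | t-test error | Wilcoxon error |
|---|---|---|---|---|
| 5% | 38 / 57 | 1.05 | about 6% | about 7% |
| 10% | 36 / 54 | 1.11 | about 8% | about 9% |
| 20% | 32 / 48 | 1.25 | about 12% | about 15%–17% |

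**Step 3: if decliners were also filled, up to N = 90.**

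| Attending | Factor | t-test, two-sided | Wilcoxon, two-sided | Wilcoxon, one-sided |
|---|---|---|---|---|
| 72 (80%) | 1.25 | 12% | about 19% | 15% |
| 60 (67%) | 1.50 | 19% | 45% | 30% |
| 45 (50%) | 2.01 | 33% | 94% | 49% |
| 30 (33%) | 3.03 | 52% | nearly 100% | 49% |

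The Wilcoxon test suffers more because the filled pairs form a block of tied differences with one sign. Attending pairs alone give about 5% throughout. Worst-value filling is no repair: with N = 90 it gives 26%, 55%, 88% and nearly 100% (Wilcoxon, two-sided).

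These are by-visit rates. The area-under-the-curve comparison uses the same fill but was not computed separately.

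**Step 4: healed areas under a literal fill.** Let reduction be normal with mean μ and SD 50, capped at 100, and a = (100 − μ)/50. The healed share is 1 − Φ(a), and the mean of unhealed areas is μ − 50φ(a)/Φ(a). Assume a control mean of 50, so the treated mean is 70:

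- healed: 15.9% of control areas and 27.4% of treated areas;
- unhealed means: 35.6 and 47.0;
- healed areas kept at 100: 61.6 − 45.8 = 15.7 points (unrounded);
- healed areas mean-filled: 47.0 − 35.6 = 11.4 points, 27% smaller.

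Control means of 40 and 60 give 16.8 to 12.6 points (25% smaller) and 14.5 to 10.3 (29% smaller). With SD 30 the shrinkage is 14% to 25%.

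A separate simulation restricted to extension patients assumed control mean 50, SD 50, correlation 0.5, a further 15-point gain by week 20 and 40% to 100% uptake. The difference fell from about 15 to about 10.7 points, and literal filling of healed areas alone gave about 8% to 9% type I error under no difference.

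**The case against.** **The analysis set.** Endpoint 2 uses areas measured on the required observation days. The extension is optional and names no such days, so a patient who never enters has no value to be missing. This stands: entrants-only is the more natural reading. A reader might infer from Step 3 that the extension tests would nearly always be falsely positive. The documents do not support that, because nowhere do they say that all 90 patients are analysed after week 10. The 94% and near-100% figures are also two-sided, whereas the sample-size hypothesis is one-sided and the corresponding rate stops near 50%.

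**Exclusion for consecutive missed visits.** If this carried into the extension, entrants who stop would be excluded and not filled. Its scope is arguable, since it follows a sentence about the ten-week period. Single missed visits would still be filled.

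**A healed area is not missing.** Its area is zero and its reduction is 100% by definition. Section 2 already stops monitoring at healing before week 10 while the primary endpoint is at week 10, so the main phase relies on the same understanding. This largely stands. A reader might infer that the plan directs healed areas to be overwritten. It does not; it only omits the convention.

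**The fault belongs to endpoint 2.** Partly true: correcting that rule would remove most of the problem. But the cross-reference is what takes the rule beyond the stated limit on missed visits.

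**The multiplicity correction protects.** It does not. Benjamini-Hochberg needs valid p-values as input.

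**Conclusion.** The concern holds in a limited form. Mean-filling followed by paired tests is a stated rule, and it makes the endpoint 5 tests anti-conservative: about 6% to 12% (t) and 7% to 17% (Wilcoxon) among entrants, assuming 40 or 60 entrants, 5% to 20% missing whole pairs at a visit, and missingness unrelated to outcome. The 12% to 52% (t) and roughly 18% to nearly 100% (Wilcoxon, two-sided) rates are conditional on filling decliners up to 90, which the plan does not specify.

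The healed-area part is an unstated convention. The 14% to 29% shrinkage is what a literal fill would do, using week 10 planning values and assumed means.

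Only optional secondary endpoint 5 is at issue. This argument gives no ground to doubt the primary week 10 analysis or the sample size, which reproduces exactly.

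**What to change.** In section 6, endpoint 5, replace the cross-reference to endpoint 2 with the following:

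- missing values are not mean-filled;
- a healed area is recorded as 100% reduction (area 0) at every later visit to week 20;
- each visit is tested on pairs with both values known, observed or healed, and the number of pairs is reported;
- the trend is assessed with a repeated-measures model of the known values, not a filled area under the curve;
- the analysis set is stated: either patients with both areas healed by week 10 are included at 100% for both, or the set is extension entrants only. The choice must be explicit because patients with both areas healed have nothing left to observe and never enter;
- results are labelled descriptive, because entry is self-selected.

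In the extension-patient simulation above, carrying healed areas at 100% gave type I error of 4.8% to 5.3% and, under the 20-point effect, a mean difference of 14.8 to 15.2 points, equal to the simulated true value in those patients.

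The cost is a few sentences of wording, with no extra patients or visits. Endpoint 5 will have fewer pairs and lower apparent precision than the filled analysis would show.
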